5.3 Study Definitions and Derived Variables

Unless otherwise specified, the duration of Week 48 analysis is defined as Study Day 1 until Week 48, as it is meant to be inclusive both of study treatments leading to the primary efficacy outcome at Week 48 and of safety assessments in that period.

Baseline values are defined as the most recent values prior to the first dose of study treatment.

5.4 Analysis Sets

The efficacy and safety analyses that are specified in Sections 7.0 and 8.0 will utilize the analysis sets as specified in this section.

5.4.1 Full Analysis Set

The Full Analysis Set (FAS) includes all patients who received any study treatment (KSI-301 or sham) and have gradable DRSS value at baseline. Patients will be analyzed according to their randomized treatment. The FAS will be used in the primary analyses of efficacy.

5.4.2 Safety Analysis Set

The Safety Analysis Set includes all patients who received any study treatment (KSI-301 or sham). Patients will be analyzed according to the study treatment they actually received.

5.5 Examination of Subgroups

The primary efficacy endpoints will be summarized in the following subgroups of baseline characteristics.

Table 2: Subgroups

[figure not shown]
Characteristics	Subgroup
Age	18-64 years of age
	65-74 years of age
	75-84 years of age
	\geq 85 years of age
	< 65 years of age
	\geq 65 years of age
	< 75 years of age
	\geq 75 years of age
Sex	Female
	Male
Ethnicity	Hispanic or Latino
5	Not Hispanic or Latino
DRSS*	Level ≤47

KS301P106 SAP Version 1.0 KSI-301 – Kodiak Sciences Inc.

Characteristics	Subgroup
	Level ≥53
HbA1c level*	$\leq 8.5\%$
	>8.5%
Investigational site*	North America
e	Rest of World
Race	White
	Black or African American
	Asian
	American Indian or Alaska Native
	Native Hawaiian or other Pacific Islander
	Other
Lens status	Aphakic
	Pseudophakic
	Phakic

Other subgroup analyses may be explored.

5.6 Multiple Comparisons/Multiplicity

5.7 Multicenter Studies

This is a multicenter, international study. Efficacy data collected from all study sites will be pooled for data analysis. The effect of study site on the efficacy analysis results may be explored, as needed.

5.8 Analysis Visit

For efficacy analyses, unscheduled or early termination visits will be assigned a study day and then mapped to the appropriate analysis window as detailed in Table 3. In the event where more than one record falls in the same analysis window, the following rules will be used in sequential order to determine the record that will be used for data analysis:

- If there is a scheduled visit (including scheduled visits from SoA-B in Appendix 1) in the analysis window, then the scheduled visit's data will be used.
- If there is no scheduled visit in the analysis visit window, the record (including records from SoA-B in Appendix 1) that is the closest to the scheduled study day at a given visit will be used.
- If there is no scheduled visit in the analysis visit window and there is a tie between the two records with regards to the number of days before and after the scheduled study day, the later record will be used.

Analysis visit windows will not apply to subject data listings. Prior to any missing data imputations or analysis, the analysis visit windows will be applied to the data.

Nominal Visit	Scheduled Study Day	Starting Day for Nominal Visit	Ending Day for Nominal Visit
Day 1	1	1	1
Week 8	56	2	98
Week 20	140	99	182
Week 32	224	183	266
Week 44	308	267	322
Week 48	336	323	364
Week 56	392	365	434
Week 68	476	435	518
Week 80	560	519	602
Week 92	644	603	658
Week 96	672	659	686

Table 3: Windows for Unscheduled Visit

Note: Nominal visits for efficacy assessments are at Day 1, Week 8, every 12 weeks from Week 20 – Week 44, Week 48, every 12 weeks from Week 56 – Week 92, and Week 96.

6.0 **BASELINE ANALYSES**

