7.1.2 Analysis of Primary Efficacy Endpoint

The primary efficacy endpoint will be estimated based on the FAS, i.e., all randomized subjects who received at least one treatment injection and have gradable DRSS value at baseline.

The statistical analysis will be performed using the Cochran-Mantel-Haenszel (CMH) method,

A 'Hypothetical' strategy will be applied for all intercurrent events where measurements after occurrence of intercurrent event will be imputed using the last observation carry forward (LOCF) procedure. For patients who develop sight-threatening complication(s) and have non-gradable value at their first visit where open-label treatment is administered, the non-gradable values will be imputed as no change from baseline. For patients without intercurrent event, missing and non-gradable values at Week 48 will be imputed using LOCF. Baseline will be carried forward if all post-baseline observations are missing or non-gradable. Non-gradable values are observations where DRSS level is 90.

The p-value will be reported for comparison between KSI-301 and sham groups. In addition, the weighted percentages difference between the KSI-301 and sham (i.e., KSI-301 – sham) and 95.02% CI of the difference will be presented. Percentages are calculated as 100×number of "responders"/number of patients in FAS. Weighted percentages are based on weighted average of observed estimates across strata using CMH weights. The CI are based on the normal approximation to the binomial proportions.

The CMH method as described for the primary efficacy analysis will be used for all sensitivity analyses below.

7.1.3 Sensitivity Analysis 1

In this analysis, a 'Composite' strategy will be applied for all intercurrent events where patients with occurrence of intercurrent event by Week 48 will be considered as non-responders. For patients without intercurrent event, missing and non-gradable values at Week 48 will be imputed using LOCF, and baseline will be carried forward if all post-baseline observations are missing or non-gradable as in the primary analysis.

7.1.4 Sensitivity Analysis 2

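### SAP 5.8 lets an ungradable scheduled Week 48 photograph displace a gradable repeat in the same window, so DRSS is carried forward although a measured grade exists

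*SAP*

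**What the plan says.** SAP 5.8 brings repeat photographs into the efficacy analysis: "unscheduled or early termination visits will be assigned a study day and then mapped to the appropriate analysis window". It then deals with competing records: "In the event where more than one record falls in the same analysis window, the following rules will be used in sequential order". The first rule opens "If there is a scheduled visit (including scheduled visits from SoA-B in Appendix 1) in the analysis window"; where that holds, the record from that visit is taken, whatever its content. Closeness to the target day, and the preference for the later record in a tie, apply only when the window holds no scheduled visit. The order of operations is explicit: "Prior to any missing data imputations or analysis, the analysis visit windows will be applied to the data".

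SAP 7.1.2 gives the status of an ungradable photograph: "Non-gradable values are observations where DRSS level is 90". For patients without an intercurrent event, "missing and non-gradable values at Week 48 will be imputed using LOCF". If no post-baseline value is gradable, baseline is carried forward. SAP 7.2.2 uses the same method for the ≥3-step endpoint. SAP 7.3 imputes nothing for the additional secondary endpoints and analyses only observed, gradable, uncensored values.

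Protocol 9.4.1 specifies only LOCF, with a baseline fallback. SAP 10.0 gives the SAP's missing-data definitions precedence over the protocol's.

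**The concern.** A level-90 photograph is an observation, so it is a record that the first rule can select. Selection precedes imputation, so a gradable repeat is set aside before LOCF runs. The eye is then analysed on an older grade, or on baseline, although its DRSS was measured inside the Week 48 window.

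The rules are also inconsistent. If the participant misses the scheduled visit, the second rule uses that same repeat. An ungradable scheduled photograph is thus handled worse than none, and the SAP gives no reason for this.

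No planned sensitivity analysis would show the effect. Sensitivity Analysis 1 keeps the same LOCF for patients without an intercurrent event. Analyses 2 and 3 repeat the primary handling with some patients excluded.

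**Working it through.** **1. The window.** The Week 48 row of SAP Table 3 is "Week 48 336 323 364": scheduled day, first day, last day. It reproduces from midpoints between scheduled days:

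- (308 + 336)/2 = 322, so the window opens on Day 323.
- (336 + 392)/2 = 364, so it closes on Day 364.

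The protocol's SoA-A allows ±7 days around Week 48, which is Days 329 to 343 when counted from Day 336. That leaves 364 − 343 = 21 days in which a later repeat still falls in the analysis window.

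**2. The rules applied as written.** Take an eye with no intercurrent event, baseline level 47, a scheduled Day 337 photograph graded 90 and an unscheduled Day 344 photograph graded 35. On the abbreviated scale in protocol Table 1, 47 to 43 to 35 is two steps of improvement.

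| Week 44 grade | Value analysed as written | Responder as written | Responder if gradable records are selected first |
|---|---|---|---|
| 47 | 47 | no | yes (35) |
| 43 | 43 | no | yes (35) |
| 35 | 35 | yes | yes (35) |
| 90, no other gradable post-baseline value | 47 (baseline) | no | yes (35) |

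With no scheduled Week 48 record at all, the rules as written select the Day 344 photograph and the eye is a responder. The error can also run the other way: a Week 44 grade of 35 followed by a repeat graded 47 would count as a response that the repeat contradicts.

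**3. Weight of one eye.** With 120 per arm, 1/120 = 0.83 percentage points.

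**4. Number of eyes.** The documents give no ungradable, retake or discordance rate, so these are assumptions: 3–5% of scheduled Week 48 photographs ungradable, half of those repeated, and 20–30% with a different responder status in the carried grade and the repeat.

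- Eyes with a displaced repeat: 240 × 0.03 × 0.5 = 3.6 to 240 × 0.05 × 0.5 = 6.
- Eyes that change status: 3.6 × 0.20 = 0.72 to 6 × 0.30 = 1.8, over both arms.
- Per arm, split evenly: 0.36 to 0.9 eyes. 0.36/120 = 0.3 points and 0.9/120 = 0.75 points.

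**5. Effect on power.** The planned response rates are redacted, so the sample size cannot be reproduced. As an illustration only, assume true response of 30% against 12%, 120 per arm and α = 0.0498. Assume also that the error only ever removes responders. Let f be the share of eyes with a displaced repeat and q the share of true responders who were already responders at the older visit. Each arm's rate is then multiplied by 1 − f(1 − q).

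- f = 0.05, q = 0: 28.5% − 11.4% = 17.1 points instead of 18.0; power 91.7% instead of 93.3%.
- f = 0.01, q = 0.8: 17.96 points; power 93.2%.

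The first case is deliberately severe: its f is twice the largest value in step 4 (5% × 0.5 = 2.5%). With 40% against 15%, the loss over the same range is at most 1.25 points and power stays at about 99%.

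**The case against.** The strongest reply is that the trigger may never occur. No document requires an ungradable photograph to be retaken. Fundus photography is not on the list recommended for unscheduled visits in protocol Appendix 5, and imaging instructions are left to the Reading Center. A retake filed under the Week 48 visit would count as scheduled data and would not be discarded. This stands as a limit on frequency. It does not change what the rule does when an unscheduled repeat exists.

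It can also be said that 5.8 does not state that unselected records are deleted, and that 7.1.2 does not define the source for LOCF. That is true. However, applying windows before imputation most naturally means that LOCF works on the selected records. A repeat taken after the scheduled visit is also not an earlier observation to carry forward.

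Three stronger readings are tempting, and the documents do not support them:

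- **BCVA and OCT are discarded in the same way.** The level-90 code is what makes an ungradable photograph a record. Nothing gives an unmeasured BCVA or OCT that status. If selection is by parameter, which the text allows, the unscheduled value is the only record and is used. The text is ambiguous here and does not establish a fault.
- **The error lowers the KSI-301 response.** In Group A the Week 44 visit is 24 weeks after the Week 20 dose, while Week 48 is 4 weeks after the Week 44 dose, so the carried grade comes from another point in the dosing cycle. The documents give no evidence that DRSS differs between the two visits.
- **An arm shifts by a point or more.** Under the assumptions above, that would require the changed eyes to fall in one arm and move the same way.

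**Conclusion.** The point holds for DRSS in eyes with no intercurrent event. Followed as written, SAP 5.8 and 7.1.2 replace a measured, gradable grade in the Week 48 window with an older grade or baseline. This affects the primary and ≥3-step endpoints, and it removes the eye from the worsening endpoints, where nothing is imputed. After an intercurrent event the primary analysis replaces later grades by LOCF whichever record is selected, so those eyes are largely outside the point.

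The effect is probably small. About one or two eyes would change over both arms under assumed rates that the documents can neither confirm nor refute, and the direction is not established. It would not by itself undermine the trial's conclusion. It merits correction because the rule treats an ungradable scheduled photograph worse than a missed visit, and because choosing the gradable record later without a prespecified rule would be a departure affecting the primary endpoint.

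**What to change.** Add to SAP 5.8, before treatment codes are unmasked for the Week 48 analysis:

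> For DRSS, in patients with no intercurrent event on or before the records concerned, selection within an analysis window is first restricted to gradable records (level other than 90). The scheduled, closest and later rules are then applied in order, and LOCF is used only if no gradable record remains in the window. The handling in Section 7.1.2 of data after an intercurrent event, and of a non-gradable first open-label visit, is unchanged.

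The restriction on intercurrent events is needed. SAP 7.1.2 assigns no change from baseline when the photograph at the first open-label visit is ungradable. The Week 48 window spans 364 − 323 + 1 = 42 days, so a diagnosis visit and the visit four weeks later can both fall inside it. An unconditional preference for gradable records could override that assignment.

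For BCVA and OCT, state only that selection is made per parameter among non-missing values.

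The cost is a few sentences of SAP text and a small change to the derivation code. No additional data are needed. Some Week 48 grades would come from photographs taken after the protocol's ±7-day visit window, which the existing rules already accept when there is no scheduled visit.

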4.1.3.1 Sight-threatening Complications of Diabetic Retinopathy in the Study Eye

Definitions and Documentation of Sight-threatening Complications

In this study, sight-threatening complications of DR in the Study Eye include DME, PDR, and/or ASNV. The protocol definition of each sight-threatening complication in the Study Eye is provided in Table 3. The diagnosis of DME, PDR, and/or ASNV will be made by the masked Investigator.

Because the treatment schedule changes for participants who develop these complications (as described below), it is very important that the imaging and/or clinical documentation described in Table 3 is collected at the time of diagnosis. It is also very important that the color fundus photographs are submitted to the reading center, because the color fundus photographs from this visit will be used for DRSS endpoint assessment.

Table 3:	Protocol KS301P106: Sight-threatening Complications of Diabetic
	Retinopathy: Definitions and Required Documentation for Initial
	Diagnosis

Sight-threatening Complication	Definition	Required Documentation		
Diabetic Macular Edema (DME)	 CST of ≥320 microns on SD-OCT and at least 5-letter decrease in best corrected visual acuity from Day 1 due to DME (as assessed by the Investigator); or 	A fundus photograph and OCT (Section 8.1.6) of the Study Eye must be obtained prior to the first treatment of DME.		
	• CST of ≥350 microns on SD-OCT due to DME (as assessed by the Investigator).			
Proliferative Diabetic Retinopathy (PDR)	 Neovascularization of the disc (NVD) or neovascularization elsewhere (NVE); Vitreous hemorrhage; or Pre-retinal hemorrhage. 	PDR must be documented with fundus photography (Section 8.1.6) [and, optionally, fluorescein angiography (Section 8.1.8)] of the Study Eye prior to initiation of the first treatment of PDR.		
Anterior segment neovascularization (ASNV)	 Neovascularization of the iris (at least two cumulative clock hours); Neovascularization in the iridocorneal angle (as assessed clinically by gonioscopy); or Neovascular glaucoma. 	A fundus photograph of the Study Eye must be obtained prior to the first treatment of ASNV. ASNV must be documented by clinical exam. Anterior segment photographic documentation is preferred if possible, but not required.		

Treatment of Sight-threatening Complications of Diabetic Retinopathy

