Participants who develop sight-threatening complications of DR in the Study Eye will be treated with open-label KSI-301 5 mg, irrespective of the treatment group that they were originally randomized into (KSI-301 5 mg or sham). The original treatment group randomization will remain masked throughout the study. Sight-threatening complications of DR in the Study Eye include DME, PDR, and/or ASNV. The diagnosis of DME, PDR, and/or ASNV will be made by the masked Investigator. See protocol Table 3 for definition of each sight-threatening complication.

CONFIDENTIAL	KS301P106 SAP Version 1.0
	KSI-301 – Kodiak Sciences Inc.

At the visit that a sight-threatening complication of DR is diagnosed (i.e., the "Dx Visit"), treatment with open-label KSI-301 5 mg will be initiated. Starting at the Dx Visit, participants will no longer follow the study visits and assessments outlined in SoA-A of Appendix 1, nor receive further masked treatments. Instead, they will follow the study visits and assessments outlined in SoA-B of Appendix 1, which is specific to the participants who develop DME, PDR, and/or ASNV.

Treatment of DME, PDR, and/or ASNV will consist of the following:

• Two doses of KSI-301 5 mg, given four weeks apart (+/- 7 days), followed by KSI-301 5 mg once every 12 weeks (Q12W; +/-14 days). Thus, the first dose shall occur during the study visit in which DME, PDR, and/or ASNV was diagnosed, and the second dose shall occur 4 weeks (+/- 7 days) later. Thereafter, subsequent doses shall occur Q12W (+/-14 days).

More frequent visits and more frequent treatments with KSI-301 5 mg and/or pan-retinal photocoagulation (PRP) are at the discretion of the Investigator if the sight-threatening complication(s) are still present. Treatment with KSI-301 5 mg may not be given more often than monthly (28 ± 7 days).

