Visit Windows (Days)		+/-7	+/-14	+/-14	+/-14	+/-14	+/-7	+/-7
Concomitant Medication Review ²	Х	Х	Х	Х	Х	X	Х	Х
AE/SAE Review	Х	Х	Х	Х	Х	X	Х	Х
General Assessments								
Vital Signs ³							Х	
Laboratory ⁴							Х	
Plasma ADA/NAB Samples (pre-injection)	х			х			Х	
Plasma PK/Biomarker Samples (pre- injection)	х			х			Х	
Pregnancy Test ⁵ (WOCBP only)	Х	Х	Х	Х	Х	X	Х	X
Ophthalmic Assessments ⁶								
BCVA ETDRS (4 meters) ⁷	Х	Х	Х	Х	Х	X	Х	
Ophthalmic Exam (Slit lamp, IOP ⁸ , dilated indirect ophthalmoscopy)	х	х	х	х	х	х	Х	
SD-OCT ⁹	Х	Х	Х	Х	X	X	Х	
Fundus Photos ⁹	Х	Х	Х	Х	Х	X	Х	
Fluorescein Angiogram ⁹	Х			Х			Х	
KSI-301 5 mg (Open-label) ¹⁰	Х	Х	Х	Х	Х	х		
Post-injection Assessments (Vision check, IOP ⁸) ¹¹	х	Х	х	Х	х	х		

Abbreviations: ADA = anti-drug antibody; AE = adverse event; ASNV = anterior segment neovascularization; BCVA = best corrected visual acuity; Dx Visit = the first study visit where a sight-threatening complication of diabetic retinopathy (DME, PDR, and/or ASNV) is diagnosed; DME = diabetic macular edema; ET=Early Termination; ETDRS = early treatment diabetic retinopathy study; IOP = intraocular pressure; NAB = neutralizing antibody; PK = pharmacokinetics; PDR = proliferative diabetic retinopathy; Q12W = once every 12 weeks; SAE = serious adverse event; SD-OCT = spectral domain optical coherence tomography; WOCBP = women of childbearing potential.

1 Dx Visit is the first study visit where a sight-threatening complication of diabetic retinopathy (DME, PDR, and/or ASNV, as defined in protocol Section 4.1.3.1) is diagnosed in the Study Eye; open-label KSI-301 treatment will be initiated at this visit.

2 Record any concomitant medication used by the participant within 30 days prior to Day 1. Procedural medications administered (e.g., dilating drops, fluorescein) will not be recorded.

3 Height and weight will be recorded at the screening visit only.

4 Clinical laboratory tests as described in protocol Appendix 2 and Table 5.

5 Urine pregnancy test will be performed locally for women of childbearing potential, prior to fluorescein angiogram and study treatment (if applicable). If urine pregnancy test is positive, it must be confirmed with a serum pregnancy test. Local urine testing will be standard for the protocol unless serum testing is required by local regulation or IRB/IEC.

6 Ophthalmic assessments will be performed in both eyes at Week 96, and only in the Study Eye at all other timepoints.

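### SAP 5.8 does not guarantee that the diagnosis-visit DRSS grade is the value carried forward to Week 48

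*SAP*

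**What the plan says.** Four provisions have to work together.

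- **Which grade counts.** Protocol 4.1.3.1 says of the diagnosis visit that "the color fundus photographs from this visit will be used for DRSS endpoint assessment". Protocol 9.4.1 censors only the grades obtained after it.
- **What happens afterwards.** SAP 7.1.2 applies a hypothetical strategy under which "measurements after occurrence of intercurrent event will be imputed using the last observation carry forward (LOCF) procedure". It adds that a non-gradable value at the first open-label visit, which is the Dx visit, counts as no change from baseline. That rule has a purpose only if the Dx grade feeds the endpoint.
- **Order of operations.** SAP 5.8 says "Prior to any missing data imputations or analysis, the analysis visit windows will be applied to the data".
- **Choice within a window.** Rule 1 in SAP 5.8 begins "If there is a scheduled visit (including scheduled visits from SoA-B in Appendix 1) in the analysis window" and takes that visit. Rule 2 begins "If there is no scheduled visit in the analysis visit window, the record (including records from SoA-B in Appendix 1) that is the closest", and rule 3 breaks ties under the same condition. Neither covers a window holding two scheduled visits.

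The next SoA-B visit follows soon after diagnosis: "the second dose shall occur 4 weeks (+/- 7 days) later". Most Table 3 windows are much wider than that, for example "Week 20 140 99 182" (scheduled day, start, end).

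**The concern.** Nothing in SAP 5.8 removes post-event records before one record per window is chosen, and nothing protects the Dx record. There are two ways to lose an unscheduled Dx grade.

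- **Dx+4-week route.** The scheduled SoA-B visit four weeks later falls in the same window and is preferred under rule 1. It follows open-label treatment, so SAP 7.1.2 replaces it by LOCF, and the value carried forward comes from the previous window.
- **SoA-A route.** A scheduled SoA-A visit attended earlier in the same window is preferred over the later unscheduled Dx record, and its older grade is carried forward.

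An eye that had gained 2 steps and lost them by diagnosis could then count as a Week 48 responder. A non-gradable Dx photograph would likewise escape the no-change rule. The endpoints at stake are the primary and the ≥3-step key secondary (SAP 7.2.2), which shares its method. The additional secondary endpoints are not imputed, so LOCF does not affect them. SAP 10.0 gives the SAP precedence on intercurrent events and missing data, so the protocol's intent may not settle the matter.

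**Working it through.** **1. Table 3 reproduced.** Each upper limit is the midpoint between consecutive scheduled days: (56+140)/2 = 98; (140+224)/2 = 182; (224+308)/2 = 266; (308+336)/2 = 322; (336+392)/2 = 364. All nine limits from Week 8 to Week 92 match.

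**2. How often Dx+28 shares the Dx window.** For a window from day a to day b, the number of such diagnosis days is (b − 28) − a + 1.

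- Week 8 (2–98): 69
- Week 20 (99–182): 56
- Week 32 (183–266): 56
- Week 44 (267–322): 28
- Week 48 (323–364): 14

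The sum is 223. Diagnosis days run from 2 to 343 (Week 48 day 336 plus its 7-day visit window), which is 342 days, so 223/342 = 65%. At +21 days it is 258/342 = 75%; at +35 days, 188/342 = 55%.

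**3. Days that can create a false response by the Dx+4-week route.** For a diagnosis in the Week 8 window, the only earlier record is baseline. LOCF then gives no change, hence a non-responder. Removing those 69 days leaves 223 − 69 = 154, and 154/342 = 45%.

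**4. Worked example (assumed grades).** Baseline 53; Week 8 = 43, a 2-step gain in protocol Table 1; unscheduled Dx on day 110 = 61 (mild PDR); Dx+4 weeks on day 138. Days 110 and 138 both lie in the Week 20 window. Rule 1 selects day 138, which is post-event, so LOCF returns to 43 and the eye is a responder. With the Dx grade kept, it is a non-responder.

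**5. Size by this route.** The documents give no switch or lost-response rates. Assume that 5% to 15% of KSI-301 eyes switch by Week 48, that 10% to 30% of those had a ≥2-step gain lost at diagnosis, that all diagnoses are unscheduled, and that diagnosis days are spread evenly.

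- Low: 0.05 × 0.10 × 0.45 = 0.2 points
- High: 0.15 × 0.30 × 0.45 = 2.0 points

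**6. The SoA-A route is not in that figure.** With SoA-A visits attended on their nominal days, a later Dx shares the window on days 57–98, 141–182, 225–266, 309–322 and 337–343: 42 + 42 + 42 + 14 + 7 = 147 days. Of these, 28 (days 141–154 and 225–238) are already among the 154, leaving 119 (119/342 = 35%). The same assumptions would add at most 0.05 × 0.10 × 0.35 = 0.2 to 0.15 × 0.30 × 0.35 = 1.6 points. This is generous, because the gain must be lost within 42 days of the visit that showed it.

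**7. Dx at a scheduled visit.** Dx+28 shares the window for Week 8 (day 84), Week 20 (168), Week 32 (252) and Week 48 (364), but not Week 44 (day 336 is in the Week 48 window). In the first four cases two scheduled records compete and 5.8 gives no rule. If closeness to the nominal day were borrowed from rule 2, the Dx record would always win for a diagnosis on a nominal day.

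**8. Direction.** The net shift is (switch × displaced × lost gain) on KSI-301 minus the same product on sham. With 10% × 100% × 50% against 30% × 100% × 10%, it is 5.0 − 3.0 = 2.0 points toward KSI-301. With 2% × 100% × 20% against 30% × 100% × 10%, it is 0.4 − 3.0 = 2.6 points toward sham. All of these inputs are assumed.

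**The case against.** The strongest reply is that SAP 5.8 does not prescribe displacement. SoA-B lists the Dx visit as its first column, and its footnote says "Dx Visit is the first study visit where a sight-threatening complication of diabetic retinopathy", so the Dx visit can itself be read as a scheduled SoA-B visit; often it is a scheduled SoA-A visit too. Rule 1 then does not rank the four-week visit above it. This stands: a reader might infer that the Dx grade is lost whenever the two visits share a window, but the text compels that only for an unscheduled Dx that is not counted as an SoA-B visit. On the other reading the SAP is silent, and the choice falls to the programmer.

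Intent is also clear from SAP 7.1.2 and the protocol. That stands as well, but the stated order of steps does not carry it out.

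The protocol calls NPDR slowly progressive and asymptomatic, so many diagnoses should fall at scheduled visits. This reduces the size in proportion. In addition, SAP 4.3.1 limits the primary analysis to data up to the Week 48 visit, which arguably excludes a four-week visit late in the Week 48 window. Dropping those 14 days leaves 140/342 = 41% and an upper figure of 1.8 points.

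Finally, Sensitivity Analysis 1 counts every eye with an intercurrent event as a non-responder, so it would expose a material effect. It does not correct the primary analysis, and Sensitivity Analyses 2 and 3 inherit the same windowing.

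**Conclusion.** The point holds as a gap between SAP 5.8 and the rule that SAP 7.1.2 and the protocol intend. For an unscheduled diagnosis, following the stated order and rule 1 can turn a progressed eye into a responder; for a scheduled one, the outcome is undefined. This should be settled before unmasking.

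By the Dx+4-week route the overstatement on KSI-301 is at most about 0.2 to 2.0 points, given the assumed rates, evenly spread diagnosis days and every diagnosis unscheduled. It is proportionally less otherwise. The SoA-A route is additional, with the looser ceiling shown above.

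Two stronger readings are not supported. A reader might apply the full 65% and obtain 0.3 to 2.9 points (0.05 × 0.10 × 0.65 to 0.15 × 0.30 × 0.65), but that counts Week 8-window days on which the four-week route can only fall back to baseline. A reader might also conclude that the error must favour KSI-301. That is probable, because more KSI-301 eyes should have an earlier gain to carry forward, but it is not certain. Sham may have more diagnoses. And DME is not a DRSS level, so an eye with DME may first show its improvement at the Dx visit and lose that response through displacement.

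**What to change.** Amend SAP 5.8 in two sentences.

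1. Before the visit windows are applied, remove DRSS records dated after the first intercurrent event, keeping the Dx-visit record.
2. In the window containing the Dx visit, use the Dx-visit record whether it was scheduled or unscheduled, and carry it forward to Week 48; if it is non-gradable, apply the no-change rule of SAP 7.1.2.

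The first sentence leaves no diagnosis day on which a post-diagnosis record competes with the Dx grade. The second also closes the SoA-A route and the case of two scheduled records in the Dx window. The cost is a short text change and a different programming order. No new data are needed.
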